3.2 Rationale for the Study Design and Dose

It is difficult to estimate the timing of response to abatacept but given the general timing of response to biologic therapy in rheumatic disease patients we anticipate that a 24-week trial is adequate in this pilot study Syn-ILD. In addition, we will employ the dose of ABT that has been used in most of the RA trials to date. For a pilot, proof of concept study we will not employ a dose escalation design.

3.3 Outcome Measures

The outcome measures used in this trial will include:

- Pulmonary Function Test - change in FVC%, FEV1%, DLCO%
- University of California San Diego Shortness of Breath Questionnaire (UCSD SOBQ)

- Qualitative changes in HRCT
- Six minute walk distance (6MWD)
- Mean daily step count on Fitbit One®.

The Myositis Clinical Core Set Measures (CSM) used in this trial are those agreed upon by IMACS include:

- The MMT-8 (Manual muscle testing)
- Patient global VAS recorded on a 10cm scale
- MD global VAS recorded on a 10cm scale
- HAQ disability index
- At least one of the muscle enzymes (CK, aspartate aminotransferase (AST), alanine aminotransferase (ALT), aldolase, lactate dehydrogenase (LDH))
- Global extramuscular disease activity (a composite of constitutional, cutaneous, skeletal, gastrointestinal, pulmonary and cardiac activity) score recorded on a 10 cm VAS scale on the Myositis Disease Activity Assessment Tool (MDAAT)

3.3.1 Primary Outcome Measures

The primary outcome criteria for efficacy will be the FVC% change from the baseline visit to week 24 between the 2 treatment arms (SOC/placebo vs. SOC/ABT). An intention to treat analysis will be used. Ranked ANCOVA will be used with average standardized rank change in the predicted FVC% as the outcome measure and the standardized rank baseline as a covariate. Primary outcome criteria for safety and tolerability will be adverse events (routine adverse events or tolerability issues and serious adverse event) between the 2 treatment arms (SOC/placebo vs. SOC/ABT). Chi-square (or Fischer exact test) and t-test (or Mann-Whitney) will be used based on data variable and distribution.

3.3.2 Secondary Outcome Measures

(SOC/placebo vs. SOC/ABT) for Syn-ILD:

- a. Time to progression free survival where progression is defined as the first occurrence of any of the following: death or lung transplant or FVC $\geq 10\%$ decline *or* FVC $\geq 5\%$ decline with DLCO $\geq 15\%$ decline.
- b. Change in dyspnea, as measured by University of California San Diego Shortness of Breath Questionnaire (UCSD SOBQ) (range 0-120, higher score is worsening dyspnea).
- c. Time to improvement in FVC% by $\geq 10\%$.
- d. Rates of death or requiring lung transplant.
- e. Other individual PFT variables (FEV1%, DLCO%)
- f. Qualitative changes in HRCT chest over 6 and 12 months in the two arms. Changes in semi-qualitative scoring of fibrosis over 6 months based on HRCT chest scan images collected from all sites and centrally read by an expert blinded radiologist, will be done as a separately and analyzed.
- g. Steroid-sparing effect (calculated using prednisone dose equivalents)
- h. Frequency of treatment failures: a) patient meeting worsening criteria or withdrawal due to worsening ILD anytime during the trial or b) FVC% worsening by 10% at 6 months, c) death or transplant within 6 months.
- i. Quantitative changes in mean Six minute walk distance (6MWD)

j. Quantitative changes in mean daily step count on Fitbit One®.

Secondary outcome criteria for myositis: Myositis response will be evaluated among patients with concomitant active myositis. Active myositis is defined based on MDAAT at baseline muscle or cutaneous skin disease activity of ≥ 3 on 10 cm visual analogue scale (VAS).

New myositis response criteria (table 1) and International Myositis Assessment & Clinical Studies Group (IMACS) definition of improvement (DOI) (given below) will be used to assess myositis response in drug + SOC vs. placebo + SOC.

IMACS DOI: 3 of 6 core set measures (CSM) improved by $\geq 20\%$, with no more than 2 CSM worsening by $\geq 25\%$ (a worsening measure cannot be the manual muscle testing (MMT)).

Table 1. New Myositis Response criteria (based on conjoint analysis continuous definition using absolute % change in six core set measures)

1000Minds Model (absolute % change)		Improvement score for each level of CSM
Core Set Measure		
MD Global Absolute % Change		
Up to $\leq 5\%$		0
$>5\%$ up to $\leq 15\%$		7.5
$>15\%$ up to $\leq 25\%$		15
$>25\%$ up to $\leq 40\%$		17.5
$>40\%$		20
Patient Global/Parent Global Absolute % Change		
Up to $\leq 5\%$		0
$>5\%$ up to $\leq 15\%$		2.5
$>15\%$ up to $\leq 25\%$		5
$>25\%$ up to $\leq 40\%$		7.5
$>40\%$		10
MMT/CMAS Absolute % Change		
Up to $\leq 2\%$		0
$>2\%$ up to $\leq 10\%$		10
$>10\%$ up to $\leq 20\%$		20
$>20\%$ up to $\leq 30\%$		27.5
$>30\%$		32.5
HAQ/CHAQ Absolute % Change		
Up to $\leq 5\%$		0
$>5\%$ up to $\leq 15\%$		5
$>15\%$ up to $\leq 25\%$		7.5
$>25\%$ up to $\leq 40\%$		7.5
$>40\%$		10
Muscle Enzyme/CHQ-PF50 Absolute % Change		
Up to $\leq 5\%$		0
$>5\%$ up to $\leq 15\%$		2.5

>15% up to <=25%	5
>25% up to <=40%	7.5
>40%	7.5
Extra Muscular VAS/DAS Absolute % Change	
Up to <=5%	0
>5% up to <=15%	7.5
>15% up to <=25%	12.5
>25% up to <=40%	15
>40%	20

Total Improvement Score is sum of score achieved in each CSM

Total improvement score \geq cut points determines Minimal, Moderate and Major Improvement

Profile	Improvement Category	Cut point on total improvement score
Adult	Minimal	≥ 20
	Moderate	≥ 40
	Major	≥ 60

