3.1.1 Study Schema

We will enroll 20 adult subjects with Syn-ILD across 5 clinical sites. We expect enrollment to be completed within 15 months. A 1:1 randomization scheme for active drug: placebo as a weekly SQ injection with their SOC for 24 weeks. All patients can then enter an optional open label follow-up after the 24-week randomized, controlled phase, during which all subjects receive 24 weeks of ABT in the same fashion as the initial study phase. This follow-up phase will assess durability, long term response and safety in patients who were in the active treatment arm while allowing the placebo arm to receive active drug, thus improving recruitment and study power.

Patient must have active ILD associated with anti-synthetase syndromes (a subset of myositis) that are being given SOC treatment for ILD. Patients could have refractory disease with flare up or new onset disease. Patient may or may not have active myositis (PM/DM). We anticipate the continued participation of all subjects in open label extension phase.

Open label phase: At the end of the active study period (week 24 closing visit), patients in either arm can enroll into the optional open-label phase of 24-week ABT therapy (125 mg SQ injection weekly).

a. **Standard of Care (SOC):** The SOC of patients with Syn-ILD includes steroids OR another IS agent OR a combination of steroid and another IS agent. Thus, we will allow steroids and/or only 1 additional IS agent. **Additional IS agent can be either mycophenolate mofetil (MMF) or azathioprine (AZA), but not both.** Patients on steroids alone can be enrolled without additional IS agent. Maximum dose allowed for MMF is 3 gms/day and for AZA is 200 mg/day. Patient should be on stable dose of MMF or AZA for 4 weeks and/or stable dose of steroids 2 weeks prior to Visit 1. Visit 1 is the time of first ABT/placebo dosing. Overall goal is to enroll patients into the trial as soon as the SOC drug has achieved stable dosing. Prednisone taper will be allowed at maximum dose of 60 mg at baseline (Visit 1), at which time a forced prednisone taper will commence as outlined below. Dose of concomitant medication cannot change throughout the phase I of the trial (24 weeks) unless safety/toxicity issues supervene.

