No other concomitant IS agent is allowed (e.g. IVIG, plasmapharesis, rituximab, methotrexate, tacrolimus, cyclosporine, other biologics. Hydroxychloroquine and pirenade **are permitted** during the trial if on a stable dose for 4 weeks prior to trial entry.

Forced steroid taper (Prednisone or other steroid in prednisone equivalent doses) in subject on a stable dose of steroid 2 weeks prior to visit 1.

a. **Steroid Tapering:** May begin within or at 1 week after beginning study drug. Goal is to taper steroid to 5 mg or lower dose within 8 weeks. Recommended daily prednisone taper (or other forms of steroid in equivalent doses)

- i. 60 mg decreased to 40 mg after 1 week
- ii. 40 mg decreased to 30 mg after 1 week
- iii. 30 mg decreased to 20 mg after 1 week
- iv. 20 mg decreased to 15 mg after 1 week
- v. 15 mg decreased to 10 mg after 1 week
- vi. 10 mg decreased to 7.5 mg after 1 week
- vii. 7.5 mg decreased to 5 mg after 1 week
- viii. Further decrease as per treating physician.

b. **Steroid at Entry:** Maximum steroid dose allowed at study entry is ≤ 60 mg/day prednisone (or other forms of steroid in equivalent doses). If on a lower dose then the tapering scheme noted above should be employed based on the entry dose. Patients not on steroids are allowed in the study and are not allowed to start new steroids unless there is a disease flare.

c. **Steroid Dosing During Flare:** If in the clinical site investigator's opinion there are complications or worsening of disease that necessitate an increase in the prednisone dose (or other forms of steroid in equivalent doses) then the smallest reasonable increase should be considered (maximum increase of prednisone equivalent of 20 mg/day is allowed). After the increase, subjects should resume the prednisone taper noted above.

Concomitant medications will remain unchanged throughout Phase I, except changes made per the rescue medication protocol. During the open label Phase II, concomitant medications adjustments are permitted even if the subject has not met the definition of worsening.

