4.5.3 Rescue Medications

If in the clinical site investigator’s opinion there are complications or worsening of disease (meeting worsening criteria) that necessitate an increase in concomitant immunosuppressive therapy the following guidelines should be followed:

- The steroid dose may be increased by ≤ 20 mg (prednisone equivalent) daily. After 2 weeks of increase the forced corticosteroid taper will commence as noted above. Such patients will remain on the trial protocol (on study drug), and it will not be considered as treatment failure.
- Requirement of additional non-steroid IS therapy or requirement of increase of steroids dose > 20 mg equivalent of prednisone for worsening ILD as rescue therapy (after initial 8 weeks of study drug) will be considered a treatment failure. Such patients can be continued on the trial protocol (on study drug) only if rescue drug include either one of them: MMF, AZA, tacrolimus, cyclosporine, IVIG, methotrexate AND maximum of one non-steroid IS

therapy is given during the trial. Steroids can be concomitantly increased with non-IS agent.

- Note if additional non-steroid IS therapy or increase of steroid dose > 20 mg equivalent of prednisone occurs <8 weeks on study drug, then these patients are not considered treatment failure as not enough time to have outcome assessment.
- Biological drugs, cyclophosphamide, plasmapheresis, are not allowed as rescue therapy and will lead to withdrawal from the trial drug/placebo protocol (i.e stopping trial drug/placebo) for safety reasons. Similarly, more than one non-steroid IS agent is not allowed as rescue therapy and will lead to withdrawal from the trial drug/placebo protocol (i.e. stopping trial drug/placebo). But all patients despite withdrawal from trial drug/placebo will be followed for at least 24 weeks for clinical evaluation. Note withdrawal from trial drug/placebo as above is not considered with withdrawal from the study.

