12.3 Methods of Analysis

Primary End Point:

The primary end point for statistical analysis will be the percent FVC changes from baseline to week 24 between the 2 treatments arms (SOC/placebo vs. SOC/ABT). Ranked ANCOVA, with average standardized rank change in the predicted FVC% as the outcome measure and the standardized rank baseline as a covariate will be used. Primary outcome criteria for safety and

tolerability will be adverse event (routine adverse events or tolerability issues and serious adverse event) between the 2 treatment arms (SOC/placebo vs. SOC/ABT). Chi-square (or Fischer exact test) and t-test (or Mann-Whitney) will be used based on data variable and distribution. Patients will be stratified for sub-analysis based on their SOC drug

Secondary Analysis (SOC/placebo vs. SOC/ABT) for Syn-ILD:

- a. Time to progression free survival where progression is defined as first occurrence of any of the following: death or lung transplant or $FVC \geq 10\%$ decline *or* $FVC \geq 5\%$ decline with $DLCO \geq 15\%$ decline. This will be done using Cox proportional hazards model and controlling for baseline demographics and $FCV\%$.
- b. Change in dyspnea, as measured by University of California San Diego Shortness of Breath Questionnaire (UCSD SOBQ) (range 0-120, higher score is worsening dyspnea), will be done using Mann-Whitney test.
- c. Time to improvement in $FVC\%$ by $\geq 10\%$. This will be done using Kaplan Meier survival curve and Cox's proportional hazards model after controlling for co-variates.
- d. Rates of death or requiring lung transplant using Chi-square (Fischer exact) test.
- e. Other individual PFT variables (FEV1%, DLCO%) similar to analysis done for primary outcome of $FVC\%$.
- f. Qualitative changes in HRCT chest over 6 months in the two arms using chi-square (or Fischer exact) test. Changes in semi-qualitative scoring of fibrosis over 6 months based on HRCT chest scan images collected from all sites and centrally read by an expert blinded radiologist, will be done as a separately and analyzed using analysis strategy similar to primary outcome.
- g. Steroid-sparing effect (calculated using prednisone dose equivalents) using paired t-test.
- h. Frequency of treatment failures: a) patient meeting worsening criteria or withdrawal due to worsening ILD anytime during the trial or b) $FVC\%$ worsening by 10% at 6 months, c) death or transplant within 6 months. Chi-square test will be used to compare between the two groups.

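### The steroid-sparing outcome has no time point or summary and is tested within patients, so read as change from entry dose it mostly reflects the forced taper common to both arms

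*Combined protocol and SAP*

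**What the plan says.** Steroid sparing is a secondary objective (section 2.2). Sections 3.3.2 and 12.2.2, item g, give the outcome as "Steroid-sparing effect (calculated using prednisone dose equivalents" with nothing on when it is measured or how doses are summarised. Section 12.3 adds only the test: "Steroid-sparing effect (calculated using prednisone dose equivalents) using paired t-test".

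The dose itself is governed by section 3.1.1, without distinction by arm:

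- Steroid may be at most 60 mg at Visit 1, "at which time a forced prednisone taper will commence as outlined below".
- On the start of the taper: "May begin within or at 1 week after beginning study drug".
- On the target: "Goal is to taper steroid to 5 mg or lower dose within 8 weeks".
- The first step is "60 mg decreased to 40 mg after 1 week", followed by weekly steps to 30, 20, 15, 10, 7.5 and 5 mg. Lower entry doses use the same scheme. Below 5 mg the treating physician decides.
- "Patients not on steroids are allowed in the study and are not allowed to start new steroids unless there is a disease flare".

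Section 4.5.3 allows a steroid rescue of up to 20 mg daily. It continues: "After 2 weeks of increase the forced corticosteroid taper will commence as noted above". Such a rescue is not counted there as treatment failure.

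**The concern.** A steroid-sparing effect can appear in dose only to the extent that dose is free to follow disease control. Here the protocol prescribes most of the fall, equally in both arms, and the rescue rule brings dose back to the same level. A paired test of entry dose against a later dose then tests whether the taper was carried out. It makes no comparison of abatacept with placebo.

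The risk is a misleading result. A large and significant fall in the abatacept arm could be reported as steroid sparing when placebo patients show the same fall for the same reason. If the arms were instead compared on unadjusted change, chance imbalance in entry dose would swamp a real difference in rescue use.

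**Working it through.** **1. The plan's own figure.** Following the section 3.1.1 steps from 60 mg, one week per step, gives 60, 40, 30, 20, 15, 10, 7.5, 5. That is seven steps: 5 mg is reached at week 7 if the taper starts at once, or week 8 if it starts a week later. The 8-week goal reproduces.

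**2. Change from entry dose.** On the fixed steps with no dosing below 5 mg, change to week 24 = 5 - entry dose, in either arm:

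| Entry dose (mg) | 60 | 40 | 20 | 10 | 5 |
|---|---|---|---|---|---|
| Change (mg) | -55 | -35 | -15 | -5 | 0 |

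**3. Trace of a rescue.** Take a patient at 5 mg given the largest steroid increase that 4.5.3 does not count as failure: 5 + 20 = 25 mg, held 2 weeks, then stepped down. The scheme has no 25 mg step, so I take the next listed dose below it. Weekly doses are 25, 25, 20, 15, 10, 7.5, then 5.

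- Return to 5 mg takes 6 weeks, so a rescue begun by week 24 - 6 = 18 is invisible at week 24. If the first step comes a week later, return takes 7 weeks and the limit is week 17.
- A rescue begun at week 19 shows 7.5 mg (10 mg on the slower reading); at week 20 it shows 10 mg (15 mg).
- Cumulative excess = 7 × (20 + 20 + 15 + 10 + 5 + 2.5) = 507.5 mg, or 507.5 + 7 × 20 = 647.5 mg on the slower reading.

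A cumulative measure would thus register what a week-24 dose loses.

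**4. What the paired test detects.** No entry-dose distribution or rescue rate is in the documents, so these are assumptions. With entry doses drawn equally from 5, 7.5, 10, 15, 20, 30, 40 and 60 mg, 10 patients per arm, no drug effect and no rescue, the paired t-test is significant in about 95% of simulated placebo arms. With entry doses of 5, 10, 20, 40 or 60 mg equally likely, it is still significant in about 84% of placebo arms when 50% of patients are rescued, and in about 80% when 70% are.

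**5. What a between-arm comparison would detect.** Assume the five entry doses above, 10 per arm, and one 20 mg rescue at a random week from 8 to 23 in 50% of placebo and 10% of abatacept patients.

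- Week-24 excess by rescue week: 0 for weeks 8 to 18 (11 of 16), then 2.5, 5, 10, 15 and 20 mg. Mean = 52.5 / 16 = 3.28 mg. Expected arm difference = 0.40 × 3.28 = 1.31 mg.
- Entry dose has mean 27 mg and variance 1145 - 729 = 416, so SD 20.4 mg. Its contribution to the SD of the arm difference = 20.4 × √(2/10) = 9.1 mg; with rescue variation the total is about 9.2 mg.

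| Between-arm measure | Ratio of expected difference to its SD |
|---|---|
| Change, unadjusted | 1.31 / 9.2 = 0.14 (simulation runs 0.12 to 0.17) |
| Change, adjusted for entry dose | about 0.8 |
| Cumulative excess over schedule | 183 mg / 88 mg = 2.1 |

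At 70% against 10% rescue, the ratios are about 0.2, 1.06 and 3.2.

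**The case against.** The strongest reply is that the documents never name week-24 dose as the outcome. That is correct. A paired test implies two doses per patient, so change from entry dose is the natural reading, but cumulative dose is not excluded. A reader might infer that the plan defines the outcome as a dose fixed by the taper; the supportable statement is that the summary is undefined.

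Three further inferences also go too far.

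- *That the objective cannot be answered, or that no test on dose change could help.* Adjusting for entry dose raises the ratio from about 0.14 to about 0.8. That is still weak, but it shows that much of the noise is an analysis choice.
- *That every steroid rescue disappears.* A patient entering on no steroid and rescued with 20 mg ends at 5 mg on the fixed steps, against 0 mg if never rescued. Rescues after week 17 or 18 show at week 24, and increases of 40 mg or more clear only if begun by about week 15 or 16.
- *That the taper fully sets the dose.* Section 3.1.1 calls the taper forced but also labels the schedule as recommended, and leaves doses below 5 mg to the physician. Failed tapers and withdrawal of the last 5 mg are real signals.

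It is also fair that this is one of ten ILD secondary outcomes in a 20-patient pilot. Even the cumulative measure has only about 45% power at 50% against 10% rescue (eight entry doses, rescue in weeks 8 to 24), against about 5% for unadjusted change. The concern survives all this, because the analysis actually specified makes no comparison of the arms.

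**Conclusion.** The point holds in limited form. Item g is undefined in time and summary, and its only stated analysis is within-patient. Read as change from entry dose, it mainly measures the taper and the entry dose, and a permitted 20 mg rescue begun by about week 17 or 18 leaves no trace at week 24 in a patient on steroids at entry. A limited signal remains, so the secondary objective is poorly answered, not unanswerable.

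The taper and rescue arithmetic follows from the protocol's own steps, given one assumption about the step down from 25 mg. The simulated percentages, ratios and power rest on assumed entry doses and rescue rates and illustrate scale only; they also leave out patients entering on no steroid, repeat rescues, failed tapers and dosing below 5 mg. The change should be made: the planned result is likely to mislead, and correcting it needs little more than wording.

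**What to change.** Leave the taper and rescue rules unchanged. In sections 3.3.2, 12.2.2 and 12.3, replace the paired t-test for item g with a between-arm comparison of:

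1. cumulative prednisone-equivalent dose from Visit 1 to week 24, either adjusted for entry dose or taken as the excess over one prespecified reference path per entry dose. The reference path serves the analysis only; fix in advance its start day and its handling of doses not on the listed steps and doses below 5 mg;
2. the proportion of patients with any steroid start or increase after Visit 1.

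State that the fall from entry dose is imposed by the protocol and is not evidence of steroid sparing.

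Two sets of statements also need reconciling by the sponsor because they affect how steroid rescue is interpreted: forced against recommended taper in section 3.1.1, and section 4.5.2, which calls patients meeting worsening criteria treatment failures, against section 4.5.3, which says a steroid rescue of up to 20 mg is not a failure.

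The cost is small. Concomitant medication is already reviewed at visits and taper compliance at calls (section 7.2); the added burden is that steroid dose changes must be dated in the CRF.

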3.3.3 Safety Outcome Measures

Safety is being assessed in one of the secondary endpoints listed above in Section 3.3.2. We will statistically compare the frequency of the following adverse events between the treatment and placebo arms.

Similarly, we will analyze the proportion of serious adverse events between the treatment and placebo arms. In addition, the number and percent of patients with AEs during the treatment period will be summarized.

3.4 End of Study

As described above, the end of the study (closing visit) is week 24 for Phase I. An optional open label phase (Phase II) with 2 additional visits 3 months and 6 months after the closing visit at week 24 have been added to assess durability of ABT response and safety. This follow-up phase will assess durability, long term response and safety in patients who were in the active treatment arm while allowing the placebo arm to receive active study drug.

